- 1) **Personalized Genomic Testing for Skin Cancer – Maximizing Utility and Reach – 05/16/17**
- (v. 10)
- 2) **IRB Review History N/A**
- 3) **Objectives**

This study will have two phases, with an added usability test after Phase I and before Phase 2. Phase 1: Cognitive Interviews in Spanish.

Phase 2: Personalized Genomic Testing for Skin Cancer (PGT-SC).

The overarching goal of this study is to learn more about how to maximize the availability, comprehension and appropriate uptake of personalized genomics among different populations in New Mexico. The proposed study has been funded as an R01 by NCI for three years.

Aim I: To examine the personal utility (that is, how does personal genomic testing help the individual) of Personal Genomic Testing for Skin Cancer (PGT-SC) in terms of short-term (three months after testing) sun protection, skin screening (i.e., behaviors), communication, melanoma threat and control beliefs (i.e., putative mediators of behavior change). Guided by Protection Motivation Theory (Robberson and Rogers, 1998), **we hypothesize that behaviors and putative mediators will be higher in those who test, compared to those who decline testing or wait-list controls.**

Aim Ia. An important challenge of personal genomics involves the potential for those who receive “negative” genetic feedback to increase risky behaviors (McBride et al., 2010). To examine this potential unintended consequence of testing, we will conduct a subgroup analysis among those who receive average risk PGT-SC findings, examining sun protection at three months as the outcome. Predictors will include baseline skin cancer threat and control beliefs, skin cancer risk factors, and demographics. These findings will be used in future studies to develop messages for groups that receive average risk feedback, which accounts for large segments of those tested for moderate risk susceptibility factors across many diseases.

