Personalized genomic testing for skin cancer (PGT-SC) is an ideal context to extend Multiplex to a new population, and new outcomes. Skin cancers are preventable, curable, very common in the general population (Lazovich et al., 2012), and disproportionately increasing in Hispanics (Rouhani et al., 2010). The NHGRI Multiplex Study offered testing for melanoma risk via the melanocortin 1 receptor gene (*MC1R*) (Wade et al., 2010) because *MC1R* is common in the general population (50% \geq 1 high risk variant) (Demenais et al., 2010), interacts with sun exposure (Udayakumar and Tsao, 2009), and confers risk (2-3 fold (Raimondi et al., 2008); consistent with most moderate risk variants), *even in those with darker skin types*. *MC1R* feedback is a promising vehicle to raise risk awareness and protective behavior in the general population, including Hispanics who are largely unaware of their melanoma risks (Friedman et al., 2994; Hu et al., 2009; Piptone et al., 2002; Robinson et al., 2011). We will conduct a randomized controlled trial examining internet presentation of the risks and benefits of PGT-SC (shown to be feasible in Multiplex) versus wait-list controls who are not offered testing, comparing personal utility and reach in a general population, English or Spanish-speaking cohort in Albuquerque, New Mexico, where there is year-round sun exposure.

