In Phase II, patients will be eligible for the study if they have been registered at a UNM Clinic for six months and assigned a primary care provider, aged >18, and are fluent in either English or Spanish. We will exclude adults that are unable to consent, individuals who are not yet adults (infants, children, teenagers) and prisoners. Pregnant women will be eligible to participate. All participants in Phase II will be consented and interviewed at 1209 University Clinic, OSIS Orthopedic Clinic at [name], the Family Medicine Clinic, the Center for Employee and Occupational Health Services, both at [name] or the North Valley Clinic. Individuals who usually attend another UNM Clinic (Atrisco Heritage Center for Family and Community Health, Northeast Heights Clinic, North Valley Clinic, Westside Clinic, Southeast Heights Center for Family and Community Health, Family Medical Center, Lobo Care Clinic, Senior Health Center, or Southwest Mesa Center for Family and Community Health) and are accompanying a patient from these Clinics will be eligible for Phase II.

6) Number of Subjects (Recruitment Target)

Phase 1: We anticipate that we will conduct cognitive interviews of **40** subjects fluent in Spanish, 20 men and 20 women, who either completed high school or did not complete high school (see phase I recruitment table).

Phase I Recruitment Table

Gender

Education	Male	Female
Completed high school/equivalent or greater	10	10
Did not complete high school or equivalent	10	10

Usability Phase: We will conduct the usability survey in **up to 10** subjects who attend the 1209 Clinic.

Phase II: We anticipate that we will conduct a baseline assessment of **650** subjects (see SOMBRA Study Flow, p. 6). They will then be randomized to a “Wait List Control Group of **120** subjects and a PGT-SC group of **530** subjects. All **530** subjects will be offered MC1R genetic testing. The “Wait List Control Group (**120** subjects) will be offered the MC1R test after the **Three Month Follow Up Questionnaire**. Accordingly, all **650** subjects will be offered MC1R testing. Of those offered, based on our prior experience, we anticipate 30-50 percent will accept an invitation for testing.

Phase II: Recruitment Tables	Ethnicity	
	Hispanic	NHW
Waitlist Controls – n = 120	60	60
PGT-SC Group – n=530	265	265

7) Recruitment Methods

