C) Baseline Assessment. All participants approached will be asked to complete a three minute Eligibility Screening and a Screening Survey to determine their interest in and eligibility for study participation, as well as basic demographics. If they are eligible and interested in study participation, the PA will fully explain the study and the participant will provide written informed consent (Consent - Number 2 and UNMHSC_HIPAA_Authorization), receiving a copy of the signed consent form. The PA will guide them to complete the Baseline Questionnaire in the clinic in a semi-private space with dedicated study computer (tablet or laptop computer).

Based on prior research, we anticipate that 30% of those approached will participate and complete the Baseline Questionnaire. Sample size estimates indicate that a total number of participants of 885 is necessary to evaluate our outcomes.

After completion of the Baseline Questionnaire facilitated by the PA, participants will receive a \$15 Target Gift card for their time and effort. They will sign a Sombra Gift Card Form and receive a Sombra Appointment Card. They will then be randomized to Group 1 - wait-list controls or to Group 2 to consider PGT-SC through a secure website (randomized and balanced across Hispanic and Non-Hispanic ethnicity, n=120 in control arm, n=530 in PGT-SC arm). "Hispanic" ethnicity will be recorded by self-report. Patients will choose Spanish or English study materials.

D) PGT-SC Invitation. (Group 2 – n=530)

Participants randomized to the PGT-SC study arm will view materials on the SOMBRA Website via Internet from a home, work, library or community-based organization computer, or alternatively through a paper version of the modules if they prefer. Internet reach in Albuquerque is >80% and WiFi is available throughout the city. All participants will be asked to consider the four educational modules regarding PGT-SC. The PGT-SC modules are:

- 1) What genetic testing can and cannot tell you,
- 2) Skin cancer and genes,
- 3) Your rights if you take part in genetic research, and
- 4) Your decision to be tested or not.

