After each module, participants will be asked to answer a series of questions regarding knowledge and satisfaction with the content of each module, and after section 4 they will be asked to register a decision as to whether they wish to have a skin cancer genetic test, or not. Participants will only be able to register a test decision if they have already read and completed the questions on the first three educational modules. Knowledge and satisfaction questions are part of each module. Those who complete these steps will receive an additional \$5 target Gift card incentive for each module for a maximum a total of \$15 in Target Gift card incentives. There is no incentive associated with the 4th module on the decision to conduct genetic testing or not.

Registration of a test decision (yes; no) is our primary assessment of "reach" in this study. We expect a minimum of 30% of participants who complete the Baseline Survey to register a genetic test decision, and that this will reach 50% in some subgroups, including those with higher literacy. Additional assessments of "reach" include completion of the baseline survey and decision to pursue PGT-SC testing (yes; no).

Those who register a decision to proceed with testing will receive a DNA buccal cell test kit with instructions (Donor Mailing Form and Specimen Collection Form), which will allow them to provide a saliva sample for genetic testing, pre-paid postage envelope, and instructions in English and Spanish for buccal cell collection. Based on The Multiplex Study, we anticipate that up to 50% of participants who consider PGT-SC will return a saliva sample for genetic testing. The Molecular Epidemiology Laboratory at UNM HSC will conduct testing; participants will receive PGT-SC results by mail (or by email, if they prefer) within one month.

We will employ state-of-the-art methods of risk communication used with high comprehension in the Multiplex Study, guided by Co-Investigator [name], who originally developed Multiplex Study risk communication materials. These materials combine verbal and pictorial displays of risk information and denominator information. We will also provide written information to clarify risk level given that individuals tend to rely on the gist of the information provided (See SOMBRA Result A for average risk individuals and SOMBRA Result B for higher risk individuals)

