Overall data processing and missing data imputation. We will first examine aspects of data quality and distributional assumptions to ensure statistical integrity and accuracy: 1) data skewness, kurtosis, and parametric assumptions; 2) intention-to-treat (ITT) principles; 3) missing data considerations; and 4) control of potentially inflated Type-I errors due to multiple statistical tests. First, data skewness and kurtosis will be examined to determine whether each variable significantly deviates from normality. If so, we will employ data transformations by taking a log or square root of the skewed variables, or by using the Box-Cox transformation or kernel estimation techniques (Diggle et al., 2002) to determine the best-fitting parametric density. Second, we assume that up to 20% of the respondents will be unreachable at our three-month follow-up assessment; missing assessments may be amenable to imputation by several powerful techniques that can handle both continuous and categorical data (Graham et al., 2997; Schafer and Olsen, 1998). A related approach is the use of Hierarchical Linear Models (HLM) (Raudenbush and Bryk, 2002) to use all available behavioral outcomes data since HLM does not carry out list-wise deletion by default, thus the statistical power loss due to missing data may be minimal. We will apply the intention-to-treat (ITT) principle (Nich and Carroll, 1997). An ITT analysis in Aim I (Nich and Carroll, 1997; Willett et al., 1998) would assume missing data is related to lack of sun protection adherence. We may use the Pattern-Mixture Model to examine whether or not missed follow-up assessments are associated with baseline characteristics with safeguards to minimize

model overfit (Hedeker and Gibbons, 1997). Finally, to control for potentially inflated type-I error rate due to multiple comparisons, analyses can also incorporate a multiple comparisons method, such as a False Discovery Rate-controlling procedure, which is more powerful than simple Bonferroni corrections.

References for Data Processing

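### Aim I's hypothesis compares people by whether they chose testing, which conflicts with the randomised offer (530 vs 120) and the ITT commitment, and no contrast is named as primary.

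*Combined protocol and SAP*

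**What the plan says.** - **Hypothesis.** Section 3, Aim I, gives one hypothesis: "behaviors and putative mediators will be higher in those who test, compared to those who decline testing or wait-list controls".
- **Design.** Section 4 (Background) describes a randomised trial of the internet presentation "versus wait-list controls who are not offered testing, comparing personal utility and reach". Section 8 C (Baseline Assessment) gives the allocation: "randomized and balanced across Hispanic and Non-Hispanic ethnicity, n=120 in control arm, n=530 in PGT-SC arm".
- **Analysis principle.** Section 13 (Data Management) states: "We will apply the intention-to-treat (ITT) principle". Its one sentence about ITT in Aim I says that such an analysis "would assume missing data is related to lack of sun protection adherence". Hierarchical linear models and false-discovery-rate control are mentioned there as options.
- **Uptake.** Section 6 says of those offered the test: "we anticipate 30-50 percent will accept an invitation for testing". Section 8 D adds: "We expect a minimum of 30% of participants who complete the Baseline Survey to register a genetic test decision". For certain subgroups, among them the more literate, it puts the figure at half. It also expects at most half of those who consider PGT-SC to send back saliva.
- **Endpoints and timing.** Section 9 lists the primary endpoints, measured at the 3-month questionnaire, but names no between-group contrast. Section 8 E counts the three months from testing, and section 11 counts them roughly from recruitment. Under section 8 F, controls are offered the test only after that assessment.

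**The concern.** Participants decide about testing after they have been randomised to the offer. Testers are therefore a self-selected part of one arm, and neither comparison in the hypothesis is protected by randomisation. The plan itself expects selection: Aim II predicts lower reach in Hispanics, section 8 D expects more registered decisions where literacy is higher, and in the section 4 pilot Non-Hispanic Whites reported more consistent sunscreen use and more provider skin examinations. Testers may thus start higher on Aim I outcomes, which is the direction hypothesised.

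The as-tested comparison and the comparison by arm answer different questions: how testers differ from others, and what the offer does. An analyst could report either as the main result and claim to have followed the plan. Participants offered PGT-SC who never register a decision, or who say yes and send no sample, have no place in the hypothesis.

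The two follow-up clocks add to the problem. Wait-list controls have no testing date before their assessment, so a clock that starts at testing cannot be applied to them.

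**Working it through.** **The plan's own figure.** Section 8 C says 885 participants are needed, but gives no alpha, power, effect size, SD or contrast. The figure cannot be reproduced and does not show which comparison was intended. The two arms sum to 120 + 530 = 650.

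**Inputs from the documents**
- Loss of 20% (section 13, upper figure): 530 × 0.8 = 424 and 120 × 0.8 = 96.
- Fraction tested, f: 0.30–0.50 (section 6). On one reading of section 8 D, half of those who register a decision return saliva: 0.30 × 0.5 = 0.15 and 0.50 × 0.5 = 0.25.

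**Assumptions not in the documents:** two-sided 0.05, SD = 1, and no true effect for the false-positive rates. Testers start d SD above non-testers. The correlation r between baseline and follow-up is 0.5–0.7.

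**Step 1: false positives, testers vs wait-list.** The wait-list arm contains would-be testers and non-testers in the same mix, so bias = d(1 − f). SE = √(1/(424f) + 1/96). The rejection rate is Φ(bias/SE − 1.96) + Φ(−bias/SE − 1.96).

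| f | Testers | SE | d = 0.1 | d = 0.2 | d = 0.3 |
|---|---|---|---|---|---|
| 0.15 | 63.6 | 0.162 | 8.2% | 18.3% | 35.1% |
| 0.25 | 106 | 0.141 | 8.3% | 18.7% | 35.8% |
| 0.30 | 127.2 | 0.135 | 8.1% | 17.9% | 34.2% |
| 0.50 | 212 | 0.123 | 6.9% | 12.8% | 23.0% |

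Example: f = 0.30 and d = 0.3 give bias 0.3 × 0.7 = 0.21 and 0.21/0.135 = 1.55, hence 34.2%.

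**Step 2: with the baseline value as covariate.** If the same gap is present at baseline, bias is multiplied by (1 − r) and SE by √(1 − r²). For d = 0.3 and f = 0.30, r = 0.5 gives bias 0.105 and 14.6%; r = 0.7 gives 0.063 and 10.0%. Over all four values of f the range is about 8–15%. In simulation (4,000 runs for each combination of f = 0.3 or 0.5 and r = 0.5 or 0.7, d = 0.3), a change score gave 4.8–5.3% when the gap was equal at both times. The randomised contrast gave 4.4–5.6%.

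**Step 3: what the randomised contrast can detect.** SE = √(1/424 + 1/96) = 0.113. At 80% power the detectable difference is 2.80 × 0.113 = 0.317 SD, unadjusted. If the offer acts only through testing, divide by f to get the effect needed in testers. Power for a 0.5 SD effect in testers uses a difference between arms of 0.5f.

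| f | Effect needed in testers | Power for 0.5 SD in testers |
|---|---|---|
| 0.50 | 0.317/0.50 = 0.63 SD | 60% |
| 0.30 | 0.317/0.30 = 1.06 SD | 26% |
| 0.25 | 0.317/0.25 = 1.27 SD | 20% |
| 0.15 | 0.317/0.15 = 2.11 SD | 10% |

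Testers vs wait-list would nominally detect 0.345 SD (f = 0.50) to 0.379 SD (f = 0.30). That contrast looks better powered for an effect in testers, but it carries the bias in step 1.

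**The case against.** **The intended analysis can be inferred.** The Background ties offer versus wait-list to personal utility, which is Aim I's own construct. Data Management lists ITT separately from missing data and commits to it without limit, so the Aim I sentence need not exhaust its meaning. This stands. A reader might infer that the plan abandons randomisation; the documents do not support that. The defect is that the Aim I wording disagrees with sections 4, 8 and 13, and no section settles which governs.

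**The bias may be smaller.** No section proposes an unadjusted, follow-up-only analysis, and the prior gap is assumed. A hierarchical model using both waves could behave like the change score, near 5% if the gap is equal at both times. This stands as a limit on the size, but the model is only an option in the plan and is not tied to this comparison.

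**Aim I asks about testing, not the offer.** That is a fair reason to estimate the effect of testing as well. It does not make a self-selected comparison a randomised one.

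**Two further inferences fail.** One might say that 371 of 530 (70%) go unanalysed because only 30% register a decision. But 30% is a stated minimum, and section 8 E follows everyone with a baseline, tested or not. Nor can 371 unregistered be combined with 30% tested unless every registrant tests, which leaves no decliners. One might also infer from the assessment-point entries in the section 9 table that beliefs and communication lack a full 3-month measure. The table is broken in extraction, the questionnaire is not included, and the lead text still lists these outcomes, so this point does not rest on them.

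**Conclusion.** The concern holds as a conflict within the plan: an as-tested hypothesis beside a randomised offer and an ITT commitment, with no primary contrast named. It should be fixed before analysis because it decides what the primary result means. That conclusion needs no numerical assumption.

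The size does. Inflation in testers versus wait-list is modest at an assumed gap of 0.1 SD and substantial at 0.3 SD, and baseline adjustment reduces but need not remove it. A reader might take the rates above 30% as the expected error of this trial. The documents give no gap, so they illustrate one assumption only.

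The conflict between the two follow-up clocks is also real and bears on the randomised contrast. The statement in section 8 G that individuals are in the study for about three months favours counting from recruitment, but does not resolve it.

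**What to change.** 1. Reword Aim I so that the primary contrast is all randomised to PGT-SC versus all wait-list controls, adjusted for the baseline value of the outcome and for ethnicity, the balancing factor. Those who never register a decision, or who say yes and return no sample, are then analysed in the PGT-SC arm.
2. Keep testers versus wait-list and testers versus decliners as secondary, labelled observational and baseline-adjusted. A complier-type estimate with arm as instrument may be added as secondary to address testing itself, noting that the modules may act without testing.
3. Reconcile sections 8 E and 11 into one follow-up clock that applies to both arms, for example from randomisation.
4. State the power limit in the plan.
5. Check separately that the 3-month entries for beliefs and communication in the section 9 table match Aim I and that section's lead text.

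**Cost.** For sun protection and screening, listed at baseline and three months, naming the contrast is wording and analysis, since everyone with a baseline is already contacted. Settling the clock may change when some follow-up calls are made. The real price is dilution: the offer must produce about 0.32 SD overall, and an effect confined to testers could easily be missed at the expected uptake. With baseline adjustment, power for a 0.5 SD effect in testers at 30–50% tested rises from 26–60% to 33–72% (r = 0.5) or 46–87% (r = 0.7). Both correlations are assumed.

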Aim II: To examine differential reach of PGT-SC across Hispanics and Non-Hispanics, and potential explanations for any differential reach. Reach is defined as the extent to which genomic testing is spread throughout the population. Reach will be measured in individuals as the consideration of the pros and cons of testing and registration of test decision. Additional assessments of reach include baseline survey completion and decision to pursue PGT-SC testing. **We hypothesize that those who are self-identified Hispanic will show reduced reach, but that differences in health literacy, health system distrust, and Hispanic sociocultural factors (Marin G, et al., 1987) including cancer fatalism (Espinosa de Los Monteros and Gallo, 2011), family health orientation (Pasick et al., 2009), and skin cancer misperceptions (Torres et al., 2014; Roman et al., 2013) will explain differences in reach between Hispanics and Non-Hispanics, and provide guidance for future PGT-SC modifications for Hispanics.**

Aim III: Among those who undergo testing, to examine (two weeks after PGT-SC test result receipt) test comprehension, recall, satisfaction, and cancer-related distress, and

whether these outcomes differ by ethnicity (Hispanic versus Non-Hispanic) or health literacy, distrust, sociocultural, or demographic factors. **We hypothesize, based on prior work delivering this intervention in primary care, we will have high test comprehension, accurate feedback interpretation, and low test distress in those who get tested (Kaphingst et al., 2012).**

4) **Background**

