All subjects who participate in PGT-SC genetic testing will receive a telephone call two weeks after results are mailed, to assess PGT-SC result comprehension and potential distress (see Two Week Risk Feedback Comprehension Assessment) and to answer any questions they may have. All those who

complete this Assessment will receive a \$5 Target Gift card as thanks for their effort. Based on prior literature documenting low levels of distress in those undergoing genetic testing for high-risk mutations, and among those found to carry *CDKN2A* mutations, we anticipate low levels of distress regarding PGT-SC feedback. Anyone who reports high distress will be referred to Clinic Director and Co-Investigator [name], who addresses distress issues regularly in the UNM clinic. If they wish, a genetic counselor will be available.

E) Three-month follow-up.

All participants who completed Baseline Assessments (whether tested or not) will be contacted for assessment by telephone three months after PGT-SC testing (Three Month Follow Up Questionnaire). Participants who complete this three-month follow up assessment will receive a \$15 Target Gift card for their valued study participation.

F) Group 1 genetic testing option.

Those 120 participants randomized to the control group will receive an offer for PGT-SC directly after the three-month follow-up assessments. They will be offered testing, and of those who pursue testing, will receive results by mail or by email, sent by the PA who enrolled them, and a two-week follow-up telephone call to assess result comprehension and potential distress.

G) Summary.

We anticipate that patients will be enrolled over an approximately 12 month period, complete assessments and receive feedback within 20 months. Thus individuals are estimated to be in the study for 3 months and the enrollment and assessment period overall will last as long as 20 months total. Primary analyses will be completed in the 6 months following the 24 months period of participation; the entire study will take 3 years.

9) Study Endpoints.

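### Aim Ia asks whether average-risk results lead to riskier sun behaviour, but it names no baseline sun protection, change measure or comparator, so as written it cannot show a fall.

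*Combined protocol and SAP*

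**What the plan says.** Section 3 (Objectives, Aim Ia) raises the worry that people who receive reassuring genetic feedback may take more risks. To examine it, the plan says "we will conduct a subgroup analysis among those who receive average risk PGT-SC findings, examining sun protection at three months as the outcome". The covariates follow: "Predictors will include baseline skin cancer threat and control beliefs, skin cancer risk factors, and demographics". The stated use of the results is then given: "These findings will be used in future studies to develop messages for groups that receive average risk feedback".

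Other sections bear on what could be done:

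- Section 9 (Study Endpoints) lists sun protection as separate 5-point items, collected at baseline and at 3 months.
- Section 8, part E, covers untested participants: "All participants who completed Baseline Assessments (whether tested or not) will be contacted for assessment by telephone three months after PGT-SC testing".
- Section 8, part F, offers wait-list controls the test only after that assessment, so they have had no genetic feedback when the outcome is measured.
- Aim I compares testers with decliners or wait-list controls and is not split by test result.
- Aim III covers "test comprehension, recall, satisfaction, and cancer-related distress", not sun protection.

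**The concern.** Whether risky behaviour increases is a question of change or of contrast: it needs an earlier level or another group. The stated analysis uses neither. It can show which average-risk recipients protect themselves less at 3 months. It cannot show whether they protect themselves less than before, or less than they would have without the result.

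This is the only analysis in the documents aimed at behavioural false reassurance. If it is followed as written, the trial could report that it examined this possible harm when the analysis could not have detected it. Aim I does not fill the gap, because a fall in average-risk recipients could be offset by a rise in increased-risk recipients within the tester group.

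**Working it through.** **1. What the stated model can detect.** The documents give no figure for Aim Ia to reproduce, so the check starts with the model. Write 3-month sun protection as Y = a + Xb + e, where X holds the listed predictors.

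- If everyone's sun protection is lower by an amount d, then Y − d = (a − d) + Xb + e. The slopes b and their tests are unchanged. Only the intercept moves, and without an earlier level or another group there is nothing to judge it against.
- If the fall varies with a predictor, the problem remains. Since Y = baseline + change, the slope of Y on X is the slope of baseline on X plus the slope of change on X. A non-zero slope may therefore reflect prior habits only.

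**2. Whether another section supplies the missing part.** The predictor list is open, so baseline sun protection is unnamed rather than excluded. Section 13 (Data Management) mentions hierarchical linear models, but as a way to handle missing data and without reference to Aim Ia. No section gives Aim Ia a change score or a comparator.

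**3. Planning numbers for a repaired analysis.** Inputs from the documents:

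- 530 in the PGT-SC arm and 120 wait-list controls (Section 6).
- Uptake, Section 6: "we anticipate 30-50 percent will accept an invitation for testing".
- Sample return, Section 8, part D: "we anticipate that up to 50% of participants who consider PGT-SC will return a saliva sample for genetic testing". This may be a further step after acceptance or may overlap with it, so both readings are shown.
- Up to 20% lost at 3 months (Section 13).

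Assumptions not in the documents:

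- An average-risk share of 50%, varied from 40% to 60%. Section 4 (Background) gives only a general-population variant frequency of 50%.
- A baseline-to-3-month correlation r of 0.4 to 0.7.

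Average-risk completers at a 50% share:

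- With the further return step: 530 × 0.3 × 0.5 × 0.5 × 0.8 = 31.8, and 530 × 0.5 × 0.5 × 0.5 × 0.8 = 53.
- Without it: 530 × 0.3 × 0.5 × 0.8 = 63.6, and 530 × 0.5 × 0.5 × 0.8 = 106.

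Wait-list completers: 120 × 0.8 = 96.

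**4. Baseline-adjusted contrast with wait-list controls.** SE = √[(1 − r²)(1/n + 1/96)] in SD units, half-width = 1.96 × SE, and power = Φ(δ/SE − 1.96) for two-sided 5%. For n = 31.8 and r = 0.4, SE = √(0.84 × 0.04186) = 0.1875, so the half-width is 0.368 and power for δ = 0.3 is Φ(−0.36) = 0.36.

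| n | r | Half-width (SD) | Power, 0.3 SD | Power, 0.5 SD |
|---|---|---|---|---|
| 31.8 | 0.4 | 0.368 | 0.360 | 0.760 |
| 31.8 | 0.7 | 0.286 | 0.537 | 0.928 |
| 53 | 0.4 | 0.307 | 0.481 | 0.890 |
| 53 | 0.7 | 0.240 | 0.690 | 0.983 |
| 106 | 0.4 | 0.253 | 0.642 | 0.972 |
| 106 | 0.7 | 0.197 | 0.847 | 0.999 |

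With a 40–60% share, n runs from 25.4 to 127.2 and the half-width from 0.401 down to 0.189. Power is then 0.31 to 0.87 for 0.3 SD, and 0.69 to over 0.99 for 0.5 SD.

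**5. Other contrasts.**

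- Average-risk against increased-risk testers, equal groups: the half-width is 0.451 (n = 31.8 each, r = 0.4) to 0.192 (n = 106 each, r = 0.7).
- Mean change within average-risk testers, 1.96 × √[2(1 − r)/n]: 0.381 to 0.147 for the same extremes.

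**6. Limits.** The return rate is stated as an upper value, so 31.8 is not a floor. Section 9 lists separate items, so SD units refer to whichever score is used. The counts are completers. Under Section 13's Aim I assumption that missing means non-adherent, 40 to 133 average-risk recipients would enter (39.8 to 132.5 before loss), and results could differ.

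**The case against.** The strongest reply is that Section 3 is a statement of aims, not a full model. The predictor list is open, Aim Ia sits under Aim I with its named comparison groups, and sun protection is collected twice, so a repeated-measures analysis with a comparator is a possible reading. The stated model also serves the one use the plan gives for its findings, message development. Both points are fair, and they make this a failure to specify rather than an exclusion. They do not close the gap, because nothing commits the analyst to a baseline level or a comparator, and without them the aim's own question goes unanswered.

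A second reply is that the repaired contrast is itself confounded, so a null result would be hard to interpret. That stands as a limit and must be reported with the result. Increased-risk testers reduce part of the problem, since they also saw the modules and received a result. Registered decliners, who must have completed the first three modules, could be added as a further comparator, though they too self-select.

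A third reply is that the 3-month anchor is inconsistent: Section 8, part E, counts from testing and Section 11 counts from recruitment. This affects how any change or contrast is read. It must be reconciled as a separate point.

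Finally, the power range for 0.3 SD is wide and rests on assumed inputs. That is correct, but the defect depends on none of those numbers.

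**Conclusion.** The concern holds. As written, Aim Ia cannot show whether sun protection fell after an average-risk result, because a uniform fall leaves every predictor result unchanged. This conclusion follows from the model's form and needs no assumed figure. The predictor analysis remains usable for message development, with the caution that unadjusted predictors may track earlier habits.

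A repaired contrast would be informative for a fall of about 0.5 SD (power about 76% to over 99%) and uncertain for 0.3 SD (36% to 85%), before any confounding. These figures assume a 50% average-risk share and a correlation of 0.4 to 0.7. They are a planning range, not a forecast.

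The plan should be changed, but this is a sub-aim, and the finding does not question the randomised comparison.

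**What to change.** Amend Aim Ia as follows.

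1. Add baseline sun protection as a covariate in the predictor model.
2. Report mean change from baseline in average-risk testers with a 95% CI, as description only, since time effects, survey reactivity or uneven enrolment could mimic change.
3. Add a contrast of 3-month sun protection between average-risk testers and wait-list controls, with a 95% CI, adjusted for baseline sun protection and for the risk factors and demographics already listed. Show increased-risk testers alongside.

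Label these contrasts non-randomised and state three limits:

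- Testers select themselves.
- Module exposure differs: "Participants randomized to the PGT-SC study arm will view materials on the SOMBRA Website", whereas wait-list controls have not been offered them by the 3-month assessment. Any benefit from the modules subtracts one-for-one from an apparent fall and could hide false reassurance.
- The MC1R result is tied to pigmentation (Section 12), which itself bears on sun behaviour.

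The cost is small. Baseline and 3-month sun protection are already collected, and the comparison groups are already followed, so only specification and analysis time are needed. The downside is that the contrast is observational and must be presented as such.
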